Micropulse laser photocoagulation avoids the excessive heating which causes visible burns, tissue necrosis, and related collateral effects¹³, while providing similar clinical benefits as conventional laser coagulation.¹⁴⁻¹⁹ However, the lack of a reliable titration for every patient and absence of visible endpoint makes it difficult for the physician to (a) know which retinal areas have been treated and (b) to ensure the adequate amount of laser energy in the treatment. In addition, the dense coverage of the retina with the sub-visible laser exposures typically requires more than 500 spots in the macula, which is difficult to accomplish without pattern scanning laser. These issues prevented acceptance of this technology in clinical practice.

We have developed the titration protocol for PASCAL laser, which ensures that pulse energy is within the range of clinical efficacy, but does not exceed the tissue damage threshold²¹ in every patient. This protocol, called EndPoint Management, has been recently tested in a clinical trial, which demonstrated its safety and efficacy in treatment of Central Serous Retinopathy²² using 30% energy settings. The trial demonstrated lack of tissue damage and excellent tissue response to the treatment, even after multiple retreatments. The average retreatment period in this trial was found to be 6 months.

We propose to use the same laser parameters for treatment of the macula in patients with early AMD to prevent drusen growth and advancement of the disease into geographic atrophy or neovascularization.

AIMS OF THE STUDY

1. To determine whether photothermal therapy (PTT) of the macula with EpM® reduces the volume of drusen in the macula.
2. To determine whether PTT decreases the incidence of advanced AMD (neovascular AMD or geographic atrophy).

The primary efficacy outcome measure will be the reduction in drusen volume in the central 3mm circle over 12, 18, 24 months in subjects treated with PTT, compared to observation alone.

The secondary efficacy outcomes after the month 12, 18, 24 of follow up will be:

- **Functional outcome:**
 - Mean change in visual acuity in both groups.
- **Anatomical outcome:**
 - Reduction of drusen growth;
 - Prevention of neovascular AMD;
 - Prevention of geographic atrophy based on OCT and FAF.

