- **Safety Assessments.** Safety of the treatment will be assessed for ocular adverse event incidence (AEs) and serious AEs (SAEs), based on the reports of the patients and examination during or between visits until the month 24 of follow up. After 24 months, subjects will then be followed for an additional 3 years for observation
- **Serious adverse events (SAEs)** will be monitored continuously.

STUDY METHODS

Design:

- Prospective, Randomized Clinical Trial (RCT).
- 24 months with an additional 3 year observation follow up period. Subjects will be seen once a year and undergo non-invasive testing.
- Total patient recruitment 56 patients.
- Number of arms: 2 arms.
- Number of patients: 28 patients in each arm.

Patient Recruitment

1. Initial Assessment

The study will enroll 56 eyes in total. Patients will be initially assessed as part of their standard management and, if fulfilling all the inclusion criteria, will be referred to a Study Investigator.

At the initial assessment, the investigator will confirm that the patient has satisfied the eligibility criteria stated in the Study Protocol (SPR) and the study will be discussed in full with the study participant (SP). If interested in participating, the SP will be given a written informed consent to take home for further consideration. The patient will have a minimum of 24 hours to decide whether or not to take part in the study. All study procedures, will be explained to the SP by the investigator or staff member. The nature of the study will be also explained to the SP together with hazards of the study procedures, including any possible adverse events. The SP will be informed that he or she is free to terminate participation in the study for any reason.

Any patient unwilling to participate at this stage will be managed as part of the appropriate routine eye care pathway.

The study patient will undergo the Examination Procedures at the Baseline visit. The data from these tests will be used for study data analysis.

2. Examination Procedures at Baseline and Follow-up visits

- (1) ETDRS best corrected visual acuity.
- (2) Slit lamp biomicroscopy: dilated fundus examination with 78D Volk lens, intraocular pressure by Goldmann applanation tonometry.
- (3) Spectral domain OCT (Cirrus SD-OCT): Macular/macular cube/Volume scan & average central retina thickness and Drusen volume.
- (4) Fundus photography and autofluorescence.

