At the end of the 24 month period there will be an additional 3 year follow up. During the 3 year follow up, there would be no active component, the subjects will be seen once per year and undergo visual acuity testing and non-invasive retinal imaging to monitor for long term effects of treatment. This should not place a significant burden on the subjects since they are typically seen every 6 to 12 months for routine follow-up.

Best-corrected visual acuity (BCVA) using ETDRS charts at a distance of 4 meters, digital fundus photography, fundus autofluorescence, ocular coherence tomography (OCT), ocular coherence tomography angiography (OCTA when available on the site) will be carried out at baseline and at each follow-up visit.

TEST, treatment	Baseline	0	1 optional	3	6	12	18	24
Laser treatment		x			x	x	x	x
ETDRS visual acuity (BCVA)	x	x	x	x	x	x	x	x
Slitlamp	x	x	x	x	x	x	x	x
OCT	X	X	X	X	X	X	X	X
OCTA*	X	X	X	X	X	X	X	X
Digital Fundus Photography	X	X	X	X	X	X	X	X
Fundus autofluorescence	X	X	X	X	X	X	X	X

*OCTA will be done if available on site

STUDY RANDOMIZATION PROCEDURE

The subjects will be allocated to each arm of the study with simple randomization method using a computer-generated randomization list and sequentially numbered, sealed, opaque envelopes (SNSOE).

After a subject has signed informed consent, their name will be written on the selected envelope by the Clinical Trials Coordinator. The 56 eyes will

be randomly allocated to one of the two arms. The computer randomization will be done by the Clinical Trials Coordinator. The randomization table will be given to an independent person, who will sequentially label 56 envelopes, and enclose the written treatment type within the envelope. The study arm will be coded numerically for each subject.

METHOD OF STATISTICAL ANALYSIS

The data will be analysed using analysis of covariance, adjusting for baseline and disease severity. Results will be presented as differences between the treatment arms with their associated 95% confidence intervals, and non-significant effects interpreted in the context of these and the limited power of the study.

SAMPLE SIZE:

We estimated our sample size based on previous comparable publications that included approximately 50 eyes on average.¹¹⁻¹²

EFFICACY MEASURES:

Primary Outcome:

- Reduction in drusen volume in arm A compared to arm B.

Secondary Outcomes:

- Mean change in visual acuity (ETDRS letters)

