- Mean change in average central retinal thickness (ACRT) after 12, 18, 24 months of follow up.
- The proportion of patients with ACRT < 300 µm on Spectral domain OCT after 12, 18, 24 months of follow up
- Conversion into GA or CNV

SAFETY MEASURES:

- Monitoring of adverse events (AEs) and serious adverse effects (SAEs) (the incidence of ocular AEs and SAEs).
- Assessment of the retinal autofluorescence to identify any laser burn.
- Signs of any laser burn identified at RPE-photoreceptors layers on DRI-OCT.

ADVERSE EFFECTS:

- Any medical incidence in patients who received laser that could be associated with the treatment delivered in the research study.
- Any temporal or transitory adverse effect that has relationship to the study therapy.

REPORTING ADVERSE EVENTS (AE) AND SERIOUS ADVERSE EVENTS

- With any AE, we will treat the SP as appropriate to prevent further complications and to potentially resolve the event.
- SAEs and AE will be reported immediately (when the subject is in the office, if possible or within 24 hours of learning of the event) to the principal investigator, study coordinator and sponsor. The SP subject will be referred for further medical treatment if required.
- Follow-up reports on AEs should indicate whether the AE is presumed to be device-related, or a result of other factors, and should be recorded on the Adverse Events Report. The Adverse Events Report should be completed each time the subject is seen during the management of the incident and at resolution of the incident.
- All AEs occurring from the time of written informed consent throughout the course of the study (end of study is defined as the end of the scan acquisition) will be recorded at the study site.
- The AE should be made to describe it in terms of a diagnosis. If a clear diagnosis has been made, individual signs and symptoms will not be recorded unless they represent atypical or extreme manifestations of the diagnosis, in which case they should be reported as separate events. If a clear diagnosis cannot be established, each sign and symptom must be recorded individually.

All the adverse events shall be recorded in detail as specified below:

Name (Type)	The common name of the adverse event that appeared shall be written down.	
Date of onset	The first date that the physician in charge found the adverse event shall be written down.	

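### Does Aim 2 need a single named time point and a written five-year analysis for conversion to GA or CNV?

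*Combined protocol and SAP*

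**What the plan says.** - AIMS OF THE STUDY gives two aims. The second concerns the incidence of neovascular AMD or geographic atrophy and states no time.
- The secondary outcome list in that section is headed "The secondary efficacy outcomes after the month 12, 18, 24 of follow up will be". Visual acuity change, drusen growth, prevention of neovascular AMD and prevention of GA sit under it. None of the three visits is called the main one.
- EFFICACY MEASURES restates the outcomes. It has "Conversion into GA or CNV" without a time, close to "Mean change in average central retinal thickness (ACRT) after 12, 18, 24 months of follow up".
- Under Safety Assessments: "After 24 months, subjects will then be followed for an additional 3 years for observation". PATIENT FOLLOW-UP says that in those years "there would be no active component", and that subjects have yearly visits with "non-invasive retinal imaging to monitor for long term effects of treatment". No outcome or analysis is named for that period.
- METHOD OF STATISTICAL ANALYSIS says "The data will be analysed using analysis of covariance, adjusting for baseline and disease severity". Results are to be given as between-arm differences with 95% confidence intervals, and the section acknowledges limited power.

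**The concern.** Conversion is the subject of one of only two aims, yet a reader of EFFICACY MEASURES alone cannot tell when it is assessed. Three stated visits plus three later yearly visits make six possible answers, and an analyst who picked among them after seeing the data could favour one. The horizon also affects how much information there is. On the Introduction's rates, more than half of the control-arm conversions expected by year 5 fall after month 24, in the years with no written analysis. Months 24 and 60 also answer different questions, because the extension has no active component. The later images are scheduled anyway, so a time-to-event analysis through year 5 looks like a free gain in precision.

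**Working it through.** **1. Is there a conflict over timing?**

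| Outcome | Time in AIMS OF THE STUDY | Time in EFFICACY MEASURES |
|---|---|---|
| Drusen volume (primary) | 12, 18, 24 months | none |
| Visual acuity | 12, 18, 24 months | none |
| Mean change in central retinal thickness | not listed | 12, 18, 24 months |
| Proportion below 300 µm | not listed | 12, 18, 24 months |
| Conversion to GA or CNV | 12, 18, 24 months | none |

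Three of the five entries in EFFICACY MEASURES have no time, and all three already have one in the aims section. The two thickness entries, which carry times, do not appear in the aims section at all. The silence on conversion therefore fits an abbreviated list and does not suggest a different horizon.

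**2. Inputs.** There is no power calculation or event target to reproduce; the 56 eyes rest on the size of earlier studies. I use 28 eyes per arm (Design) and cumulative conversion of 8.6%, 16.4% and 23.5% at one, two and three years (Introduction). My assumptions are a hazard ratio (HR) of 0.5, a constant hazard carried on to year 5, no loss to follow-up and independent eyes.

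- Hazard: h = −ln(1 − 0.235)/3 = 0.0893 per year.
- Control risk, 1 − exp(−h·t): 0.1635 at year 2 and 0.3601 at year 5.
- Treated risk, 1 − exp(−0.5·h·t): 0.0854 and 0.2001.
- Expected events (28 × risk): 4.58 v 2.39 at month 24, and 10.08 v 5.60 at year 5. The control ratio is 10.08/4.58 = 2.2, and (10.08 − 4.58)/10.08 = 55% of control events come after month 24.

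**3. Precision on the hazard-ratio scale.** The interval is HR × exp(±1.96 × √(1/e₀ + 1/e₁)), where e₀ and e₁ are the expected events per arm.

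- Month 24: SE = √(1/4.58 + 1/2.39) = 0.80, interval 0.10 to 2.39.
- Year 5: SE = √(1/10.08 + 1/5.60) = 0.53, interval 0.18 to 1.40.

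This interval narrows, but the plan does not call for a hazard ratio.

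**4. Precision on the planned difference scale.** SE = √[p₀(1 − p₀)/28 + p₁(1 − p₁)/28], where p₀ and p₁ are the control and treated risks.

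- Month 24: difference −0.078, SE 0.0876, half-width 1.96 × 0.0876 = 0.17, interval −0.25 to 0.09.
- Year 5: difference −0.160, SE 0.1181, half-width 1.96 × 0.1181 = 0.23, interval −0.39 to 0.07.

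The interval widens. The expected difference grows faster, so difference/SE rises from 0.89 to 1.35, still well short of 1.96.

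**5. Power at HR 0.5.** Large-sample formulae give about 15% at month 24 and 28% at year 5. With so few events an exact test is the safer guide. Summing the binomial probabilities of every table with Fisher p ≤ 0.05 gives 5% and 18%. If the effect vanished completely after month 24, simulated log-rank power at month 60 would be 8–9%, below the 15% at month 24.

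**6. Choice among time points.** The chance of at least one p < 0.05 under no effect, by simulation with independent eyes and no loss:

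| Visits tested | Log-rank | Fisher exact |
|---|---|---|
| Months 12, 18, 24 | 10.0% | 2.5% |
| All six, 12 to 60 months | 14.8% | 6.5% |
| Months 24 and 60 | 8.4% | 4.0% |

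Most of the apparent inflation at the three stated visits comes from a large-sample test applied to about seven to nine events, not from having three visits.

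**The case for a change.** The strongest case for a change is that AIMS OF THE STUDY still leaves three visits of equal standing and does not say how years 3 to 5 count. Naming month 24 would cost one sentence, and the imaging to month 60 is already scheduled. A second criticism is that analysis of covariance, the only method named, is not the natural choice for a yes/no outcome at any visit.

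All of this stands as a description of what is missing. It does not show that the plan would mislead:

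- Month 24 is already the last stated efficacy visit, so naming it would record what an analyst would do anyway.
- The extension is introduced under safety, as observation and monitoring, which points to descriptive use.
- An analyst faced with a binary outcome and an instruction to report differences with 95% intervals would give a risk difference, allowing for fellow eyes in opposite arms (Patient Recruitment).
- The extra precision at year 5 depends on moving to a hazard ratio, power stays low, and a fading effect would reverse the gain.

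Full fading straight after month 24 is an extreme case, since the visit table marks laser at that visit. Conversely, continued full benefit to year 5 is equally unproven.

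**Conclusion.** No change follows. The timing of conversion is given once, at months 12, 18 and 24, and left out of a shorter list that also leaves it out for the primary and visual acuity outcomes. The missing main time point and the unwritten year 3–5 analysis are gaps of detail in a secondary outcome that has little power at any horizon: about 5% at month 24 and 18% at year 5 by exact test. Followed as written, the plan yields conversion differences with 95% intervals at stated visits, read in the light of admitted low power, and that is not a wrong result. A sentence naming month 24 and calling later conversions descriptive would do no harm, but it is optional.

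The figures rest on the Introduction's rates applying to these eyes, an assumed hazard ratio of 0.5, a constant hazard beyond year 3, no loss and independent eyes. With 10% yearly loss, simulated log-rank power at HR 0.5 falls to about 12% at month 24 and 21% at year 5, so attrition would shrink the gain further.

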Causal relation	Write down probable causes, and classify the causal relation with the test device depending on the presence or absence of the causal relationship as defined below. The adverse events that are judged to have no relation with the test devices are classified as complications; all the others are classified as adverse device effects.	
	Probably not related	The adverse event is definitely related to other than the test device. (Complication)
	Possibly related	The adverse event is possibly related to the test device; the causal relationship with the test devices is fully undeniable. (Adverse device effect)
	Probably related	The cause of the adverse event cannot be located. However, the adverse event is probably related to the test device. (Adverse device effect)
	Definitely related	The adverse event is definitely related to the test device. (Adverse device effect).
Severity	The severity shall be classified into mild, moderate and severe based on the criteria:	
	Mild	The symptom is mild and expected to heal soon.

	Moderate	The symptom is described as neither mild nor severe.
	Severe	The finding is serious and expected to interfere with the subject's daily life depending on the subject's physical predisposition or the circumstances under which the adverse event appeared.
Symptom, progress and treatment	Necessity for treatment and progress from the detection of the adverse event and the determination of outcome shall be written down.	
Outcome	The classification into "healed", "unchanged", "aggravated", or "death" and the outcome date shall be written down. If the subject died, statement of death shall be made.	
Views on the adverse event	Views on the adverse event by the physician in charge shall be written down. Omission is allowed if there are no special comments.	

POTENTIAL RISKS:

- Complications of conventional laser therapy including marked vision loss, paracentral scotomas or accidental application of laser in the fovea. There is limited data regarding potential risks of photothermal therapy, however, due to its non-damaging nature, it is expected to be safer than conventional photocoagulation.

STUDY PATIENT DISPOSITION

Completed SP: A completed SP is one who has not been discontinued from the study and has completed all study related procedures.

Discontinued SP: SP may be discontinued prior to their completion of the study due to:

- subject request
- adverse events
- protocol violations

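### The adverse-effect definition conflicts with the rule to record all AEs, and the causality scale contradicts its own labels, so the device-effect count depends on who reads it

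*Combined protocol and SAP*

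**What the plan says.** **Definition.** The Adverse Effects section of the combined protocol and SAP has two limbs. The first is "Any medical incidence in patients who received laser that could be associated with the treatment delivered in the research study". The second is "Any temporal or transitory adverse effect that has relationship to the study therapy". Both require a relation to treatment; only the first is limited to patients who received laser.

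**Recording.** The next section, on reporting AEs and SAEs, records "All AEs occurring from the time of written informed consent throughout the course of the study". It adds: "Follow-up reports on AEs should indicate whether the AE is presumed to be device-related, or a result of other factors". It does not say what an AE is.

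**Safety measure.** Safety Measures lists "Monitoring of adverse events (AEs) and serious adverse effects (SAEs) (the incidence of ocular AEs and SAEs"). The Safety Assessments bullet near the aims says "Safety of the treatment will be assessed for ocular adverse event incidence (AEs) and serious AEs (SAEs"). Neither names an arm, and neither says how the counts are to be tabulated.

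**Causality.** The Causal relation row of the adverse-event table makes events judged unrelated to the device complications, and every remaining event an adverse device effect. It then gives four levels, each with its class in brackets. *Probably not related* (complication) is defined as "The adverse event is definitely related to other than the test device". *Possibly related* (adverse device effect) opens with wording that matches its label, then adds that "the causal relationship with the test devices is fully undeniable". *Probably related* (adverse device effect) says that the cause cannot be located but is probably the device. *Definitely related* (adverse device effect) matches its label.

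**The concern.** There are two separate problems.

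The first is capture. The only text that says what counts as adverse is restricted to related events and, in one limb, to laser recipients. Arm B gets a sham with the aiming beam only, and the protocol does not say whether that counts as having received laser. Site staff who take the definition as their instruction may record less in Arm B than in Arm A. A sham control helps in judging harm only if events are collected in the same way in both arms.

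The second is classification. The scale decides whether an event is reported as a device effect. Where a label and its definition point to different classes, two careful assessors can put the same event in opposite columns. The Potential Risks section says that data on the risks of this therapy are limited, so the count of device effects is one of the results that readers will look for.

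**Working it through.** The documents state no AE rate, no expected number of device effects and no power for safety. There is no figure to reproduce, and the check is a comparison of texts.

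**Step 1: capture.** Each kind of event is set against the three pieces of text.

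| Event | Definition, limb 1 | Definition, limb 2 | Recording rule |
|---|---|---|---|
| After consent, before any treatment | No | No | Yes |
| Laser patient, could be associated with treatment | Yes | If related to study therapy | Yes |
| Laser patient, unrelated | No | No | Yes |
| Sham-only patient, could be associated with the procedure | Only if sham counts as laser | If related, and if sham counts as study therapy | Yes |
| Sham-only patient, unrelated | No | No | Yes |
| Sham eye of a bilateral patient, could be associated with treatment | Yes, because the patient received laser in the other eye | If related to study therapy | Yes |

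The recording rule accepts every row. The definition rejects every unrelated event and leaves the sham-only related event open. The two texts therefore conflict, and the outcome depends on which one a site follows.

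**Step 2: causality.** Each degree of suspicion is classified twice: by the labels with their bracketed classes, and by the definitions together with the rule that every event not judged unrelated is a device effect.

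| Assessor's view | By label | By definitions and that rule |
|---|---|---|
| Another cause is established | Complication | Complication |
| Device unlikely, not excluded | *Probably not related*: complication | Not definitely due to something else and not undeniable, so no level fits; adverse device effect |
| Device possible, cannot be ruled out | *Possibly related*: adverse device effect | Not undeniable, so the level's second clause fails; adverse device effect by the general rule |
| Device probable | Adverse device effect | Adverse device effect |
| Device definite | Adverse device effect | Adverse device effect |

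The second row is a direct contradiction: one event, two classes. The third row reaches the same class either way, but an assessor who must tick a level and takes the word undeniable seriously may fall back to *Probably not related*, which gives a complication. The strict reading of the lowest level therefore raises the device-effect count, and the strict reading of *Possibly related* can lower it. The direction is not fixed.

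**Step 3: scale.** With 28 per arm (Design section), moving one eye between classes changes that arm's proportion with a device effect by 1/28 = 0.036, or 3.6 percentage points, provided that the eye has no other device effect. How many events would move is not known.

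**The case against.** The strongest reply is that the document can be read coherently. Adverse effects and adverse events stand under separate headings; AEs could be all events and effects the related subset. Recording begins at consent, before any treatment, so it cannot be meant for laser recipients only. Follow-up reports must allow for causes other than the device, and the table has a complication class for unrelated events. Neither provision would have a purpose if only related events were collected. This stands, and it is why under-capture in the sham arm is possible rather than shown. It does not settle the matter, because the document never states the distinction and blurs it itself: Safety Measures pairs adverse events with serious adverse effects, while the Safety Assessments bullet speaks of serious AEs.

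A reader might infer that the sham arm must show no adverse events by definition, and that the comparison of harm is therefore wrong. The documents do not support this. The second limb has no laser-recipient restriction, the recording rule covers everyone from consent, and a bilateral patient's sham eye belongs to someone who did receive laser. No between-arm safety test is specified either, so a significance calculation would rest on event counts that the documents do not supply.

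On causality, the reply is that every level carries its class in brackets and that the word undeniable looks like a slip. The mapping does exist, and the slip is plausible. But the bracketed mapping resolves the unlikely event only for a reader who follows the label and ignores both the definition and the rule above it.

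It is also fair that evidence for a non-damaging treatment does not rest on AE counts alone. Laser burns are sought on autofluorescence and OCT as separate safety measures, and conversion to GA or CNV is a secondary outcome.

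**Conclusion.** The concern holds in two parts of different strength. The adverse-effect definition and the recording rule are in conflict, which leaves room for unequal capture between arms; nothing in the documents shows that it will happen. The causality scale is wrong as written: two of its four definitions contradict their labels, and an event that is unlikely but not excluded as device-related falls into opposite classes depending on which text is followed.

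Beyond the per-eye scale shown above, neither the size nor the direction of a miscount can be derived. That would need AE rates and the share of events in the unlikely range, and the documents give neither. It would be going too far to say that the errors favour the laser: under-capture in sham and a strict reading of the lowest level would both make laser look worse, while a strict reading of *Possibly related* could make it look better. The finding rests on the text alone, with no assumption about event rates. It should be corrected before safety data are classified and tabulated.

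**What to change.** 1. State that an AE is any untoward medical event in a participant in either arm, from written consent onward, whether or not it is related to treatment. Keep adverse device effect as the related subset, and use event and effect consistently, including for SAEs.
2. State that AEs are collected in the same way in both arms. Tabulate ocular AEs and SAEs by randomised arm and by eye. List non-ocular events by patient: someone with one eye in each arm cannot be assigned to an arm for these, and the documents do not address this.
3. Reword the causality definitions to fit their labels. For example, not related could mean that another cause is established, and possibly related that a relation cannot be ruled out. Give unlikely-related events an explicit place.
4. Keep the bracketed classes, and make them and the general rule above them agree on where an unlikely-related event goes.

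The cost is protocol and case-report wording. The small downside is a few more minor events to list for Arm B. If events have already been classified under the present scale, those at the two lowest levels should be reviewed against the new wording, blind to arm where possible.
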